Encouraging Blood Donation in Patients With a Blood Type in Short Supply

NCT05135325

April 27, 2022

Statistical Analysis Plan

Brief summary

As of November 2021, partly due to the COVID-19 pandemic, there has been a months-long national shortage of several types of blood in the U.S. (O-Pos, O-Neg, A-Neg, B-Neg, and AB-Neg), which has extended to a local blood shortage within the Geisinger footprint encompassing central and northeast Pennsylvania. The broad aim of this healthcare operations quality improvement project is to determine whether a message indicating that a patient's own blood type is in short supply increases the likelihood that they will donate, compared to a message that mentions a blood shortage without referencing the patient's blood type, or no message at all. Scientists in Geisinger's Behavioral Insights Team (BIT), part of Geisinger's Steele Institute for Health Innovation, will collaborate with Miller-Keystone, where Geisinger refers patients who wish to donate blood and from whom Geisinger receives blood for clinical purposes. Patients with one of the needed blood types will be randomized to receive 1) a message about a blood shortage that does not specify the blood types in short supply or their own blood type (no-blood-type message), 2) the same message modified slightly to specify the recipient's blood type, and to mention that their blood type is in short supply (blood-type message), or 3) no message beyond normal system messages (shortage control group). A second no-contact control group of patients without any of the needed blood types will also be observed (no-shortage control group). Both the blood-type and no-blood-type messages are informed by behavioral science, emphasizing supply needs in local hospitals and providing community-relevant examples of why someone might need blood (e.g., farming or industrial accidents). With respect to the blood-type message, informing the recipient that they have one of the needed blood types may additionally increase their perception that they are in a semi-unique position to help someone in need as compared to a more general message that may suffer from a diffusion of responsibility effect. The BIT will compare how many patients in each group choose to donate blood. They hypothesize that: 1) patients who receive either message will be more likely to donate than patients who receive no message; and 2) patients who receive the blood-type message will be more likely to donate than those who receive the no-blood-type message.

Project status

The team had originally planned to enroll 20,000 patients per arm, and 80,000 patients total. However, the study team decided to stop the study with just under 15,000 patients per arm due to logistical constraints.

Specifically, reaching the target sample size would have required us to enroll many patients who live far from existing Miller-Keystone donation sites and far from the Danville and Bloomsburg areas where Miller-Keystone often runs blood drives. Due to staffing shortages, it was not feasible to set up the additional blood drives that would have been required to enroll these patients and reach the original target sample size.

As of 4/25/2022, enrollment is complete with eligible patients that live near an existing Miller-Keystone donation site or near Danville or Bloomsburg, where Miller-Keystone ran blood drives for patients in the study. The final sample includes total of 59,093 patients.

The team has extracted primary-outcome data for the first group of participants enrolled. The data were extracted in order to set up a data pulling and sharing protocol with Miller-Keystone. However, these initial data have not yet been analyzed, and data for patients enrolled subsequently have not yet been extracted. Additionally, data collection for some participants is ongoing. We plan to extract the remaining primary outcome data all at once on or after 6/6/2022, 6 weeks following the final message send date (4/25/2022).

With the final sample size of at least 14,772 patients per arm, we will have 80% power to detect an increase in donation rates from 1% to 1.35% between any two study arms, a 35% difference, with a two-tailed alpha of .05. With our original planned sample size of 80,000 patients (~20,000 per arm), we would have had power to detect a smaller increase, from 1% to 1.3%.

Sample and randomization

The sample includes Geisinger patients who have a blood type recorded in their electronic health record, are age 18 or older, and do not have a low hemoglobin test result (<12.5) recorded in the 3 months before the patient list was extracted.

For logistical purposes, we are running this study in several phases. We have already begun the study in patients living within 20 miles of Miller-Keystone's Pittston Donor Center based on their home ZIP code recorded in their electronic health record. In collaboration with Miller-Keystone, we will create a plan for expanding the study to other geographic areas within Geisinger's service area.

For each geographic location where we run the study, we will first identify all patients from our list who meet our inclusion criteria above. Then, patients who have a blood type in need (A-, B-, AB-, O-, O+) will be randomized into the **3 shortage blood-type groups**.

A randomly-selected group of patients without a needed blood type will be selected from the patient list within that geographic area for a fourth **No-shortage control** group of the same size as each of the shortage groups listed above.

In order to encourage donation in as many patients with needed blood types as possible, we plan to send messages to those in the shortage control group at a delay (after the primary outcome time frame has passed). The patients in this group will also be randomized to receive either the no-blood-type or the blood-type message.

Planned analyses

Primary outcome

Number of Participants Who Attended a Donation Appointment

Attended a donation appointment within 6 weeks of their message send date, regardless of whether they donated. This outcome includes patients who were unable to donate for any reason (e.g., low hemoglobin) or patients who showed up to the appointment but decided to leave before donating.

[Time Frame: Within 6 weeks of the final message send date]

Question 1: Are patients who receive either message more likely to donate compared with patients who do not receive a message?

Analysis 1: We will test the hypothesis that patients who receive a message donate at higher rates than patients who do not receive a message by running an OLS regression with a binary predictor variable indicating whether or not patients were sent a message.

Question 2: Is blood donation higher in patients who receive a message that includes their blood type and mentions that their blood type is in need compared with a message that does not mention their blood type?

Analysis 2: We will test the hypothesis that patients who receive the blood-type message will be more likely to donate than those who receive the no-blood-type message by running an OLS regression with a binary predictor variable indicating whether patients were sent the blood-type message or the no-blood-type message.

Notes about timeframes and analysis

Messages sent to patients within a geographic location will be divided into separate message dates so as not to overwhelm appointment scheduling at Miller-Keystone. Timeframes listed above refer to the amount of time elapsed from the send date for a given patient. For instance, the primary outcome timeframe is 6 weeks; thus, for the purposes of this study, a patient will be counted as having donated if they donated blood within 6 weeks of their message send date.

Patients in both control groups will be divided into separate message dates, each assigned to one of the message-date groups for the experimental arms. Each control group will be monitored for appointments and donations during a date range that is aligned with the date range for its corresponding experimental group.

All analyses will exclude patients who scheduled their appointment prior to their message send date.

Sensitivity analyses and robustness checks

The analyses above will be run using a time frame of 6 weeks from the message send date. However, as a robustness check, we will rerun *Analysis 2* on the subset of patients who open the messages, using a time frame of 6 weeks from the date each individual patient opened their message.

We will run an additional robustness check including only patients who scheduled an appointment within the 2 weeks following their message send date.

As another robustness check, we will remove all patients who live within 20 miles of Danville, PA, as these patients are likely to be health care workers. They are therefore more likely to already know their blood type and/or to know their blood type is in short supply.

Recent work suggests that OLS regressions are appropriate in randomized experiments with binary outcome variables such as ours (Gomilla, 2021). However, as a robustness check, we will also run the regressions described above as logistic regressions instead of OLS regressions.

Secondary outcomes

We will use the approaches described in *Analyses 1* and *2* above to evaluate the impact of the intervention on the secondary outcome measures listed in the pre-registration:

1. Number of Participants Who Successfully Donated Blood

Attended a donation appointment within 6 weeks of their message send date and successfully donated, excluding patients who were turned away from or left their appointment without donating.

[Time Frame: Within 6 weeks of the final message send date]

2. Number of Participants Who Scheduled a Blood Donation Appointment

Scheduled an appointment within 2 weeks of their message send date.

[Time Frame: Within 2 weeks of the final message send date]

3. Number of Participants Who Scheduled a Blood Donation Appointment

Scheduled an appointment within 6 weeks of their message send date.

[Time Frame: Within 6 weeks of the final message send date]

Additional exploratory analyses

1. Household members

Patients who donate after receiving messages may also encourage members of their household to donate. We will run a negative binomial regression to test whether the number of donors residing at the same address as each target patient varies as a function of experimental group, whether the target patient donated or not, and the interaction between these variables.

2. First time donors vs. repeat donors

We will evaluate whether message effectiveness differs based on whether the patient has previously donated blood at Miller-Keystone. To this end, we will run an OLS regression model, testing whether donations vary as a function of experimental group, a bivariate indicator for whether or not the patient has previously donated blood, and the interaction between these variables.

3. Geographic location

Patients in certain geographic regions may be more receptive to our messages than others. We will test for differential effectiveness as a function of geographic region by running an OLS regression including a dummy coded predictor variable coding for geographic region (as defined by our separate outreach campaigns). We will test for an interaction between region and experimental group on donation behavior. If the interaction is significant, we will run post-hoc comparisons to probe for differences in the efficacy of our interventions separately by geographic region. If the interaction is not significant but the main effect of region is, we will run post-hoc tests on this main effect to understand how donation behavior differs by region.

Importantly, our messages are being sent on different dates in geographic regions (with some overlap), and blood donation patterns vary across the year. To control for variation in blood donation, we will attempt to determine standard donation rates across time, and to include this variable as a covariate in our analysis.

4. Time to donation

We will run regression models to test whether either intervention message influenced the timing (time elapsed since the message was sent) of donations.

5. Type of donation

We will test whether there are differences in donation type (particularly whole blood and

red blood cell donations) as a function of experimental group.

6. Demographics

We will run regression models to test for main effects of several demographic factors on donation behavior, along with interactions between these factors and message group. These demographic factors include binned age (18-24, 25-34, 35-44, 45-54, 65+), sex, race, ethnicity, line of insurance (as a proxy for socioeconomic status), and Charlson Comorbidity.

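### The broad aim and power statement cover blood-type message versus no message, but no primary, secondary or robustness analysis names that contrast

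*SAP*

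**What the plan says.** - **Aim (SAP, Brief summary).** The project asks whether the blood-type message raises donation "compared to a message that mentions a blood shortage without referencing the patient's blood type, or no message at all". The same section adds: "The BIT will compare how many patients in each group choose to donate blood".
- **Hypotheses (Brief summary).** There are two. The first is that "patients who receive either message will be more likely to donate than patients who receive no message"; the second is that the blood-type message outperforms the no-blood-type message.
- **Power (Project status).** "With the final sample size of at least 14,772 patients per arm", the SAP claims 80% power for 1% versus 1.35% "between any two study arms", at two-tailed .05.
- **Analysis 1 (Planned analyses, Question 1).** OLS "with a binary predictor variable indicating whether or not patients were sent a message".
- **Analysis 2 (Planned analyses, Question 2).** OLS with a "binary predictor variable indicating whether patients were sent the blood-type message or the no-blood-type message".
- **Secondary outcomes.** The SAP reuses both models here: "We will use the approaches described in *Analyses 1* and *2* above to evaluate the impact of the intervention on the secondary outcome measures".
- **Robustness checks.** These rerun the same regressions on subsets, with another time window, or as logistic models.
- **Additional exploratory analyses.** Several models include experimental group, but no coding or contrast is given.

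**The concern.** The aim names a specific message and, as one comparator, no message. The power statement is pairwise. The named analyses contain one pooled contrast and one message-versus-message contrast, so the comparison of the blood-type message with the shortage control has no named test.

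Neither planned test settles it alone. Analysis 1 can be positive because of the no-blood-type message only. Analysis 2 can be positive because the no-blood-type message lowered donation: at assumed rates of 1.00% (control), 1.00% (blood-type) and 0.70% (no-blood-type), Analysis 2 has about 80% power although the blood-type message does nothing relative to silence. A positive pooled result could also be reported as support for each message, when it estimates only their average.

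**Working it through.** **Inputs.** From the SAP: 14,772 per arm, 1% and 1.35%, two-sided .05. Assumed: all other rates, and the shortage control as the only comparator in Analysis 1, because the SAP does not say which control group enters.

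**Formula.** Two-proportion normal power = Φ[(d − 1.96·SE0)/SE1], where d is the difference in rates, SE0 uses the pooled rate and SE1 the separate rates.

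**The SAP's own figure.** 1.00% versus 1.35%, 14,772 each: d = 0.0035; SE0 = √(0.01175 × 0.98825 × 2/14,772) = 0.001254; SE1 = 0.001254. Power = Φ[(0.0035 − 0.002458)/0.001254] = Φ(0.83) = 79.7%. The stated 80% reproduces, for a pairwise test.

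**Graded effects: 1.00% / 1.17% / 1.35%** (control / no-blood-type / blood-type)
- Analysis 1: pooled message rate (1.17 + 1.35)/2 = 1.26%, n = 29,544, against 1.00%, n = 14,772. d = 0.0026, SE0 = 0.001085, SE1 = 0.001045. Power = Φ[(0.0026 − 0.002127)/0.001045] = Φ(0.45) = 67.5%.
- Analysis 2: 1.17% versus 1.35%. d = 0.0018, SE0 = SE1 = 0.001298. Power = Φ[(0.0018 − 0.002544)/0.001298] = Φ(−0.57) = 28.3%.
- Direct contrast, blood-type versus control: 79.7%, as above.

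**Other scenarios, same formula**

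| Control / no-blood-type / blood-type | Analysis 1 | Analysis 2 | Direct contrast |
|---|---|---|---|
| 1.00 / 1.00 / 1.35% | 37.6% | 79.7% | 79.7% |
| 1.00 / 1.35 / 1.35% | 89.4% | 5% (no difference) | 79.7% |
| 1.00 / 1.00 / 1.70% | 89.4% | over 99.9% | over 99.9% |

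**What the two planned tests imply jointly.** With equal arms, blood-type minus control = Analysis 1 coefficient + half the Analysis 2 coefficient. In the graded case, 0.26 + 0.18/2 = 0.35 percentage points. So if both tests are significant in the positive direction, the missing contrast is implied. The two contrasts are close to independent, so the chance of this is about 0.675 × 0.283 = 19% with graded effects and 0.376 × 0.797 = 30% if only the blood-type message works, against about 80% for the direct test.

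**Sensitivity to the comparator.** If both control groups entered Analysis 1, each at 1%, its power would be 84.8% in the graded case and 53.6% if only the blood-type message works. The no-shortage group is not part of the randomisation, and Analysis 2 and the direct contrast are unchanged.

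**The case against.** The strongest reply is that the plan is coherent: the two analyses map one to one onto the two numbered hypotheses, which make the broad aim specific. Pooled-versus-control plus message-versus-message is a standard orthogonal pair for three arms. The phrase on any two arms can be read as a statement of precision, not a promise to test every pair. All of that stands; the mismatch is with the aim sentence and the power statement only.

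A reader might infer that the plan would miss a working blood-type message. The figures do not support that. If only that message works (1.35%), Analysis 2 has about 80% power, at least one planned test is significant in about 87% of trials, and the direct contrast is the only significant result in about 4% of simulated trials. At 1.70%, Analysis 2 would almost always show that the messages differ, so a misleading pooled result would rarely go unnoticed. Even with graded effects, at least one planned test is significant in about 77%.

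A reader might also infer that no outcome of the two tests could answer the aim, or that the information is lost. Neither is so: two positive results together imply the contrast, and it can be computed from the two coefficients. The exploratory models could also yield such a coefficient, but they do not prespecify it. What is missing is a named estimate with its own interval and test.

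**Conclusion.** The concern holds as a gap between the stated aim and the named contrasts. It does not invalidate Analyses 1 and 2, and the plan could not fairly be said to leave the trial unable to detect a message effect.

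The cost is clearest with graded effects, the ordering the two hypotheses together allow. There the omitted contrast is the best powered of the three (about 80%, against 68% and 28%), and the only pattern in the planned tests that implies it has a chance of about 19%. These figures rest on the assumed 1.17% rate and on the shortage control as sole comparator in Analysis 1. With both control groups pooled, Analysis 1 would no longer be weaker than the direct contrast in that scenario, but it would still estimate the average of the messages. The correction is worth making because it is cheap, and Project status says that the outcome data extracted so far had not been analysed.

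**What to change.** Keep Analyses 1 and 2 as planned. Add one OLS model on the three randomised shortage arms, with one indicator for each message and the shortage control as reference. Report blood-type versus control and no-blood-type versus control with confidence intervals, labelled as prespecified supporting contrasts; the difference between the two coefficients is the Analysis 2 contrast. Apply the same model to the secondary outcomes. State that a positive Analysis 1 supports the average message effect, not each message separately. The alternative is to narrow the aim and the power statement to the contrasts actually tested.

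The cost is SAP wording, one regression on data already planned, and one or two more reported contrasts. If family-wise control is wanted, every contrast, including the pooled one, must be gated on the 2-df global test. Leaving the pooled test outside the gate gives a simulated family-wise error of about 7.5% when no message works. Full gating lowers pooled power from about 90% to 82% when both messages give 1.35%, and direct-contrast power from 80% to about 69–76% across the scenarios with a blood-type rate of 1.35%. Reporting the new contrasts as supporting estimates avoids that loss.

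### As worded, the 2-week robustness check keeps only patients who booked, so it compares show-up among bookers and cannot confirm a message effect that works through booking

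*SAP*

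**What the plan says.** The check is a single sentence under Sensitivity analyses and robustness checks: "We will run an additional robustness check including only patients who scheduled an appointment within the 2 weeks following their message send date". It names no outcome, no model and no analysis to rerun, and it does not say whether patients who did not book stay in the denominator.

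Four other places bear on it:

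- **Primary outcome:** "Attended a donation appointment within 6 weeks of their message send date, regardless of whether they donated".
- **Secondary outcomes, item 2:** "Scheduled an appointment within 2 weeks of their message send date". The secondary outcomes are there "to evaluate the impact of the intervention on the secondary outcome measures listed in the pre-registration".
- **Notes about timeframes and analysis:** "All analyses will exclude patients who scheduled their appointment prior to their message send date". This is a genuine sample exclusion that depends on scheduling date.
- **The check that follows:** "As another robustness check, we will remove all patients who live within 20 miles of Danville, PA". This too is a patient subset, as is the check on message openers that comes before.

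**The concern.** The SAP uses the same event, booking within 2 weeks, both as a result of the message and as a condition for entering the analysis. A patient who attends has normally booked first, so booking lies on the path from message to attendance. Once the sample is limited to bookers, the regression on attendance asks whether those who booked turned up. That is not the question in Analysis 1 or Analysis 2. The bookers in each group are also no longer comparable by randomisation, because a message may bring in people who differ from those who would have booked anyway.

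Because the result is called a robustness check, it invites a wrong reading either way. A real effect of the planned size would usually look fragile. A positive or negative result could reflect only a difference in who was prompted to book.

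**Working it through.** **1. The SAP's own figure.** Project status claims "80% power to detect an increase in donation rates from 1% to 1.35% between any two study arms", with 14,772 per arm and two-sided alpha 0.05.

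- SE = √[(0.01 × 0.99 + 0.0135 × 0.9865) / 14,772] = 0.001254
- z = 0.0035 / 0.001254 = 2.79
- Power = Φ(2.79 − 1.96) ≈ 0.797

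The stated 80% reproduces.

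**2. Split attendance into two steps.** Attendance rate = booking rate × show-up among bookers. The SAP gives no booking or show-up rates, so these are assumptions:

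- show-up among bookers is 60% to 90%;
- every attended appointment was booked within 2 weeks;
- the comparator in Analysis 1 is the shortage control group.

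Analyses 1 and 2 are treated as separate scenarios, each with 1.00% vs 1.35% attendance.

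**3. Who is left.** Bookers = n × attendance rate / show-up.

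- 1% group: 14,772 × 0.01 / 0.90 = 164, up to 14,772 × 0.01 / 0.60 = 246.
- 1.35% group, Analysis 2 (n = 14,772): 222 to 332.
- 1.35% group, Analysis 1 (both message arms, n = 29,544): 443 to 665.

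About 98-99% of patients are dropped.

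**4. What the bookers-only comparison estimates.** With equal show-up in both groups, the expected difference is exactly zero, although the true effect on attendance is +0.35 points.

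Now let the additional bookers whom the message prompts have a different show-up rate. Example: 80% for usual bookers and 60% for prompted bookers.

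- Booking rate without the effect: 0.01 / 0.80 = 0.0125
- Additional bookings: 0.0035 / 0.60 = 0.00583
- Show-up among bookers in the higher group: 0.0135 / (0.0125 + 0.00583) = 73.6%
- Difference: 73.6% − 80.0% = −6.4 points

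**5. Simulation.** 20,000 trials per scenario, OLS with a binary predictor, pooled variance, two-sided 0.05, usual show-up varied from 60% to 90%.

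With all patients kept, the result is significant in the right direction in 89-90% of trials (Analysis 1) and 79-81% (Analysis 2). With bookers only:

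| Show-up of prompted bookers | Mean difference (points) | Significant, Analysis 1 | Significant, Analysis 2 |
|---|---|---|---|
| Same as usual | about 0 | 2.4-2.9% favourable | 2.4-2.6% favourable |
| 10 points higher | +2.3 to +2.4 | 9-17% favourable | 8-13% favourable |
| 10 points lower | −2.8 to −3.0 | 11-14% negative | 10-13% negative |
| 20 points lower | −6.2 to −6.9 | 41-50% negative | 34-43% negative |

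In the equal show-up row, the favourable rate is essentially the one-sided false-positive rate of 2.5%.

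**6. The alternative construction.** Keep all patients and count attendance only if it was booked within 2 weeks. If 100%, 80% or 60% of attendances are booked that early in both groups, the result is significant in the right direction in 89%, 82% and 69% of trials (Analysis 1) and 80%, 71% and 59% (Analysis 2).

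**The case against.** The strongest objection is that the sentence may not define an analysis set at all. The definitions of the primary outcome and of secondary outcome 1 speak of including or excluding patients when they mean which events count, and nobody leaves the denominator. The section opens with time frames, so a 2-week booking window could be one more variation of that kind. The neighbouring checks state their subsets more explicitly, and a check that discards nearly everyone is an unlikely intention. This stands as a plausible account of what the authors meant. It does not rescue the text. The sentence names patients as what is included and no outcome, and an analyst who followed it would filter the data set. In the planning case with equal show-up, the two readings detect the same true effect in under 3% or in roughly 80-90% of trials, and the SAP does not choose between them.

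A second objection is that little depends on this check. Analyses 1 and 2 are untouched, no rule lets the check overturn them, and booking is tested separately as secondary outcomes 2 and 3. That is correct, and it limits the weight of the point.

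A third is that the show-up rates are assumed and the scenarios lean towards sign reversal, with no case of prompted bookers attending 20 points more often. That is fair. At usual show-up of 60%, that case gives 0.0135 / (0.01/0.60 + 0.0035/0.80) = 64.2%, a difference of +4.2 points. The direction cannot be known in advance. That the check fails to test the stated hypotheses does not depend on any of these values.

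**Conclusion.** The concern holds for the sentence as written. Restricting the sample to patients who booked within 2 weeks conditions on a post-randomisation outcome, and the check then does not test the hypotheses of Analyses 1 or 2. If the planned effect works wholly through booking and show-up is equal, the expected difference is zero and favourable significance falls from about 80-90% to under 3%. If prompted bookers differ in show-up, the estimate moves up or down for reasons unrelated to whether the message raised attendance.

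The sizes rest on the assumed show-up range, on all attended appointments being booked within 2 weeks, and on attendance being the outcome of the check, which is the natural reading. The logical point needs only the last of these. The correction should be made, but it concerns a supporting analysis and leaves the primary results intact.

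**What to change.** Replace the sentence with one that moves the 2-week rule from the sample into the outcome. For example: *Analyses 1 and 2 will be rerun on the same patients, with the outcome equal to 1 if the patient attended within 6 weeks of the send date at an appointment scheduled within 2 weeks of that date, and 0 for all other patients.* This is sound whichever meaning was intended.

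If the comparison among bookers is still of interest, keep it separately, label it descriptive show-up among bookers, and do not present it as a robustness check.

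The cost is one sentence of SAP wording, with the same data and the same regressions. Project status says that the first data extracted had not been analysed and that the rest had not been extracted, so at the SAP's date the change could still be prespecified.

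### The exploratory prior-donor and region interaction tests are on the additive scale only, because the logistic check stops before them and the SAP does not say on which scale message effectiveness is compared

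*SAP*

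**What the plan says.** Analyses 1 and 2 are OLS regressions with one binary predictor; Analysis 1, for example, is done by "running an OLS regression with a binary predictor variable indicating whether or not patients were sent a message". Under Sensitivity analyses and robustness checks, the SAP defends this choice ("Recent work suggests that OLS regressions are appropriate in randomized experiments with binary outcome variables such as ours") and adds a logistic version: "we will also run the regressions described above as logistic regressions instead of OLS regressions". Everything above that sentence is Analysis 1, Analysis 2 or a rerun of them on a subset or with another time window. None has an interaction term.

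The tests of effect modification follow under Additional exploratory analyses:

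- **Item 2, prior donation.** The aim is "We will evaluate whether message effectiveness differs based on whether the patient has previously donated blood at Miller-Keystone", and the method is "we will run an OLS regression model, testing whether donations vary as a function of experimental group, a bivariate indicator" for prior donation, with their interaction.
- **Item 3, region.** The method is "running an OLS regression including a dummy coded predictor variable coding for geographic region" and its interaction with experimental group. The result has a consequence: "If the interaction is significant, we will run post-hoc comparisons to probe for differences in the efficacy of our interventions separately by geographic region".
- **Item 6, demographics.** Main effects are tested "along with interactions between these factors and message group", but the type of regression is not named.

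Nowhere does the SAP say whether a difference in effectiveness means a difference in percentage points or in ratios. Its power statement under Project status uses both: a rise from 1% to 1.35%, also described as a 35% difference.

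**The concern.** For a plain two-arm contrast the choice of scale does not affect whether there is an effect: a zero risk difference is also a ratio of one. An interaction is different. If the message has an effect and two strata start from different rates, equal ratios and equal differences cannot both hold. The SAP therefore applies its scale check where scale matters least and leaves it out where scale can decide the conclusion.

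Prior donation is a factor for which unequal baseline rates are to be expected. A significant OLS interaction there could be read as the message persuading repeat donors better, when it has multiplied attendance equally in both groups. The reverse can also happen: equal absolute gains give no OLS interaction although the proportional effect in first-time donors is larger. For region, a significant interaction also opens region-by-region comparisons of efficacy. Robust standard errors do not remove the issue, because it concerns the quantity being compared.

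**Working it through.** **The plan's own figure.** Inputs from Project status: 14,772 per arm, 1% against 1.35%, two-sided alpha 0.05.

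z = 0.0035 / √[(0.01×0.99 + 0.0135×0.9865)/14,772] = 0.0035/0.001254 = 2.79; power = Φ(2.79 − 1.96) = 79.7%. The stated 80% is reproduced.

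**Inputs for the illustration.** From the SAP: 14,772 per arm (so 29,544 messaged patients against 14,772 shortage controls) and the ratio 0.0135/0.01 = 1.35. Assumed, because the SAP gives no stratum figures: 10% prior donors, attending at 5% in the reference arm, and the same risk ratio of 1.35 in both strata. The reference arm is taken at 1% overall, whether it is the shortage control or the no-blood-type message. Experimental group is reduced to one two-group contrast at a time.

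**Rates.** Never-donors: (0.01 − 0.10×0.05)/0.90 = 0.556%, a nine-fold baseline difference. With the message: prior donors 5% → 6.75% (+1.75 points); never-donors 0.556% → 0.75% (+0.194 points). Additive interaction: 1.75 − 0.194 = 1.556 points.

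**OLS interaction, messages against control, heteroskedasticity-correct variance:**

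- prior donors: 0.05×0.95/1,477.2 + 0.0675×0.9325/2,954.4 = 5.346×10⁻⁵
- never-donors: 0.00556×0.9944/13,294.8 + 0.0075×0.9925/26,589.6 = 0.070×10⁻⁵
- SE = √(5.416×10⁻⁵) = 0.00736; z = 0.01556/0.00736 = 2.11; chance of significance = Φ(2.11 − 1.96) ≈ 56%.

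For message against message, with 14,772 in each arm, SE = 0.00870, z = 1.79, chance 43%.

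**Logistic interaction, same data.** Log odds ratios are 0.319 (prior donors) and 0.302 (never-donors). For messages against control the difference of 0.017 has SE 0.196, so z = 0.085 and the chance of significance is about 5%. Message against message also gives about 5%.

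**Sensitivity to the assumptions** (OLS interaction, correct variances):

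| Case | Messages vs control | Message vs message |
|---|---|---|
| 10% prior donors at 5%, ratio 1.35 | 56% | 43% |
| 10% at 7%, ratio 1.35 | 78% | 63% |
| 5% at 5%, ratio 1.35 | 29% | 22% |
| 10% at 9%, ratio 1.35 | 90% | 79% |
| 10% at 5%, ratio 1.20 | 23% | 18% |
| 10% at 5%, ratio 1.10 | 10% | 8% |
| two-fold baseline, 5–20% prior donors, ratio 1.35 | 8–15% | 7–12% |
| equal baselines | 5% | 5% |

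The third and fourth rows are the lowest and highest feasible cases for shares of 5%, 10% and 15% with prior-donor rates of 5% to 12% in whole points. Combinations in which prior donors alone would reach or exceed the 1% overall rate are excluded. The 90% case is extreme: never-donors are then at (0.01 − 0.009)/0.90 = 0.11%.

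**The reverse case.** Give both strata +0.35 points. Prior donors go from 5% to 5.35% (ratio 1.07) and never-donors from 0.556% to 0.906% (ratio 1.63). The OLS interaction is exactly zero.

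**The case against.** The best argument on the other side is that an additive interaction is a legitimate target. A message that adds 1.75 points among prior donors and 0.19 among others yields about nine times as many extra attendances per message sent, and for an operations project seeking donations that is a real difference. In the illustration the additive interaction is truly non-zero, so the 56% and 43% are power and not a false-positive rate. This stands. A reader might infer that the OLS tests are invalid, or that a difference should be claimed only when it appears on both scales; the SAP gives no basis for either.

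Three further limits also stand:

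- The stratum rates are assumed, and the result depends strongly on them and on the size of the effect. A reader might infer that the plan *will* report spurious differences; the most that can be said is that it *could* report a uniform proportional effect as a differential one. For region, where baselines may be closer together, the chance may be small.
- A reader might extend the point to demographics. The SAP says only that regression models will be run there, so additive-only is not supported for that item.
- The tests are exploratory. No primary or secondary conclusion depends on them, and nothing stops the authors from tabulating stratum rates.

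What the objection does not answer is that the SAP states an aim in terms of effectiveness without a scale, and drops for these tests a check that it uses elsewhere.

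**Conclusion.** The point holds for two exploratory analyses, prior donation and region. By its wording and position the logistic check does not reach them, both are fixed as OLS interactions, and the scale of comparison is not declared. A uniform proportional effect could therefore be described as differential effectiveness, or a real proportional difference could go unseen.

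Under the assumed inputs and a risk ratio of 1.35, the OLS interaction is significant in roughly 29% to 90% of trials (messages against control) or 22% to 79% (message against message) when prior donors attend at 5% or more. At a two-fold baseline difference this falls to about 7% to 15%, and it is lower for smaller effects; the logistic interaction stays near 5% to 6%. Severity is low. The main analyses and the use of OLS for them are not called into question.

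**What to change.** Extend the logistic check to exploratory analyses 2 and 3. For each stratum, report the attendance or donation rate by arm, the risk difference, and the risk or odds ratio, with confidence intervals. Whenever a difference in effectiveness is claimed, name the scale, for example a larger absolute gain with a similar proportional gain.

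The cost is a few extra model fits on data already to be held, and some interactions will have to be reported as scale-dependent. When the SAP was written no outcome data had been analysed, so the scale could be set without knowledge of results.
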